1. AMENDMENT HISTORY

Amendment No.	Protocol Version No.	Date issued	Author(s) of changes	Details of Changes made

2. SYNOPSIS

Study Title	SHOCkwave lithotripsy for Calcified plaques in patients with peripheral arterial disease: a pragmatic registry with in-depth automated plaque analysis – the SHOCC study.				
Study Design	Prospective multicentre cohort study				
Participants	 Adult patients with Peripheral Arterial Disease (PAD) and Chronic Limb Threating Ischaemia (CLTI) referred to secondary care, who undergo Intravascular Lithotripsy (IVL) as part of their standard NHS care. Clinicians performing the intravascular lithotripsy procedure on study participants 				
Planned Sample Size	Main study: 60 patients. Sub study participants: 20. Clinicians: 10.				
Follow-up duration	Six (6) months.				
Planned Study Period	Start date: 01/10/2021 Study end date: Twenty one (21) months after start date. • 3 months for NHS sites' set up and regulatory approvals • 9 months for recruitment and imaging analyses • 6 months for follow-up • 3 months for analyses and dissemination				
	Overall duration of the study: Twenty one (21) calendar months.				
Primary Aim and Primary Objective	Primary objective: Investigate the effect of intravascular lithotripsy on the patency of a lower limb atherosclerotic lesion in patients with symptomatic PAD treated in the NHS, six months after the procedure.				
Secondary Aim(s) and Secondary Objective(s)	1. To investigate whether patients require further angioplasty or other procedures in the six months post intravascular lithotripsy. 2. To investigate whether patients suffer any of the following complications; stroke, transient ischaemic attack, myocardial infarction, or lower limb amputation in the six months post intravascular lithotripsy. 3. To investigate whether patients are readmitted to hospital for PAD related treatment in the six months post intravascular lithotripsy. 4. To investigate whether changes in atherosclerotic plaque consistency are observed within three days post intravascular lithotripsy 5. To gather information about how and why clinicians decided upon this choice of treatment over alternative methods available in the NHS.				

Primary Endpoint/Outcome Measure	Primary outcome measure: patency of the treated arterial atherosclerotic lesion based on duplex ultrasound measurement at six months after the procedure has taken place (recorded as a binary outcome i.e. yes or no).
-	·
	requiring re-intervention or having additional imaging due to re-stenosis (secondary outcomes)
	Patients' quality-of-life.

3. ABBREVIATIONS

AE Adverse event
AR Adverse reaction
CI Chief Investigator

CLTI Chronic Limb Threatening Ischaemia

CRF Case Report Form

EC Ethics Committee (see REC and / or NHS REC)

GCP Good Clinical Practice
GP General Practitioner
IC Intermittent Claudication
ICF Informed Consent Form
NHS National Health Service

NIHR National Institute for Health Research
NRES National Research Ethics Service

IVL Intravascular Lithotripsy

PAD Peripheral Arterial Disease or Peripheral Artery Disease

PI Principal Investigator

PPI Patient and Public Involvement

PIL/S Participant/ Patient Information Leaflet/Sheet

R&D NHS Trust R&D Department

SC Study Co-ordinator

REC Research Ethics Committee

SAE Serious Adverse Event
SAR Serious Adverse Reaction
SOP Standard Operating Procedure

SUSAR Suspected Unexpected Serious Adverse Reactions

SMF Study Master File

SSC Study Steering Committee

UK United Kingdom

4. BACKGROUND AND RATIONALE

Peripheral Arterial Disease (PAD) affects a fifth of people over the age of 60 in the United Kingdom (UK)(1-3). It is the commonest cause of lower limb amputation(4). Patients with PAD who develop symptoms present either with pain when walking, called intermittent claudication, or chronic limb threatening ischaemia, a condition characterised by constant pain in the leg and/or gangrene. More than half of patients who have chronic limb threatening ischaemia or intermittent claudication are expected to die, have an amputation or a major cardiovascular event i.e. heart attacks or strokes, within five years (2, 5-8). The number of people with PAD is expected to rise in the next few years, due to a sedentary life-style, poor dietary choices, rising prevalence of diabetes and longer life-expectancy(3, 9, 10).

Approximately 5% of individuals between the age of 55 and 74 have intermittent claudication or chronic limb threatening ischaemia in the UK (1, 2, 6-8, 10). In patients with chronic limb threatening ischaemia the one-year risk of limb amputation is 30% and five-year all-cause mortality is 50%, similar to various advanced forms of cancer (1, 2, 5-8, 11). Patients with chronic limb threatening ischaemia require urgent revascularisation (restoration of blood flow) in order to save their leg (prevent amputation). Overall, 27,465 leg amputations took place in patients with PAD between 2015 and 2018 in the UK(12). A timely and successful lower limb revascularisation is required to prevent these amputations and subsequent impact on patients' autonomy, quality-of-life and future health problems(3, 5, 16, 17).

An angioplasty is a procedure where an artery is opened using wires and balloons. It is the most common procedure offered to patients with PAD, especially those with limb threatening ischaemia, and it is recommended by international guidelines(18). Many factors can affect how long the arteries treated with angioplasty can remain open for(19). Calcium in the artery is one of the main factors which might cause a new blockage in an artery treated with angioplasty(20). Our research group has previously reported that the percentage of calcified plaque independently predicts restenosis at one year after angioplasty and the absolute volume of calcium was associated more amputation(23).

Intravascular lithotripsy has been developed as an adjunct to plain balloon angioplasty and stenting for severely calcified arterial plaques in patients with PAD. This device (produced by Shockwave Medical) shatters the calcium within the atherosclerotic plaque into tiny particles using ultrasound (energy) via a standard angioplasty balloon. The assumption is that applying intravascular lithotripsy makes the plaque more compliant and hence the plaque responds better to angioplasty. It has been approved by the Medicines and Healthcare products Regulatory Agency (MHRA) in the UK and is used routinely for coronary artery procedures. It is licensed for treatment of lower limb vessels in the UK and Europe. A recently completed randomised controlled trial involved 306 lesions (stenoses or occlusions of femoral or popliteal arteries or both) treated with either intravascular lithotripsy and angioplasty or conventional means (full data under publication) showed a 79% reduction in dissection(s) of the artery (which would have required a stent to treat), and a 69% reduction in using further angioplasty (i.e. more balloons) to treat the disease. This study only presented information up to 30 days after surgery, which is not sufficient to draw conclusions about longer-term performance of this technology. There is also no high-quality multicentre clinical data, from a study conducted within the NHS regarding the use of this technology in patients with PAD, especially those with chronic limb threatening ischaemia.

Intravascular lithotripsy has the potential to greatly improve the treatment of patients with calcified atherosclerotic plaques and severe PAD, since it might decrease the need for

stenting (associated with increased costs and the complications listed above), decrease the duration of the procedure, limit the need for re-intervention, reduce the possibility of peripheral embolisation, and overall improve long-term clinical results i.e. reduce the chance of amputation.

Before, proceeding to a large-scale randomised study across the whole of the NHS, this current study will provide us with valuable information in order to plan such future studies, including: clinical performance of this technology in patients with severe PAD and chronic limb threatening ischaemia (a group of patients who have very calcified arterial disease), mechanistic information as to how the plaque responds to intravascular lithotripsy, information about clinicians' equipoise and feasibility of performing a randomised study and the number of eligible patients seen at NHS centres treating patients with PAD. Further, this prospective multi-centre cohort study will provide important clinical information for patients treated with intravascular lithotripsy in the NHS, including: patency after treatment with this technology, additional treatments used with the intravascular lithotripsy, amputation free survival, duration of hospital stay, and number of re-interventions. This is vital information in order to be able to plan a future high-quality randomised assessment of clinical effectiveness in the NHS. As far as the mechanistic elements of intravascular lithotripsy are concerned, we have pioneered and validated a detailed analysis of atherosclerotic plaque composition using 3 dimensional plaque analysis, based on computed tomographic imaging. This allows us to calculate with extreme precision the volume and proportion of calcium, fibrotic tissue, fat and other extracellular constituents within any atherosclerotic plaque. Using this technique in the SHOCC study, we will be able to quantify what exactly happens to the atherosclerotic plaque after applying intravascular lithotripsy and therefore provide mechanistic evidence for this technology, which is currently non-existent. Again, this is vital information before proceeding to further randomised clinical assessments of the technology. Finally, even though intravascular lithotripsy is now commercially available in the NHS, we still do not know how clinicians (surgeons and radiologists) decide who to treat with this technology. We will attempt to answer that question using information collected during the SHOCC study.

5. OBJECTIVES

Primary objective:

Investigate the effect of intravascular lithotripsy on the patency of a lower limb atherosclerotic lesion in patients with symptomatic PAD treated in the NHS, six months after the procedure.

Secondary objectives:

- 1. To investigate whether patients require further angioplasty or other procedures in the six months post intravascular lithotripsy.
- 2. To investigate whether patients suffer any of the following complications; stroke, transient ischaemic attack, myocardial infarction, or lower limb amputation in the six months post intravascular lithotripsy.
- 3. To investigate whether patients are readmitted to hospital for PAD related treatment in the six months post intravascular lithotripsy.
- 4. To investigate whether changes in atherosclerotic plaque consistency are observed within three days post intravascular lithotripsy
- 5. To gather information about how and why clinicians decided upon this choice of treatment over alternative methods available in the NHS.

6. STUDY DESIGN

6.1 Summary of Study Design

Patients: Patients with chronic limb threatening ischaemia or severe claudication and femoropopliteal or below-the knee arterial occlusion or stenosis, amenable to treatment with endovascular means and intravascular lithotripsy.

Intervention: Intravascular lithotripsy of an atherosclerotic plaque; this is part of the patients' standard NHS care. This study is observational in nature (i.e. no additional intervention is offered to these patients). The indication(s) for use of intravascular lithotripsy will have been discussed in the Departments' Multidisciplinary Team Meeting(s) and patients will have been consented for the procedure(s) accordingly.

Outcomes: all complications during the in-hospital stay, at thirty days and six months will be documented, including: patency of the treated arterial lesion (primary outcome of interest), reintervention, lower limb amputation; change in the treated atherosclerotic plaque consistency for patients requiring re-intervention or having additional imaging due to re-stenosis (secondary outcomes). Further, all intra-operative details, including additional treatments, will be recorded.

Study design: multicentre prospective cohort study. Non-randomised research. Standard NHS care will be provided to patients as per current National Institute for Health and Care Excellence for PAD. A sub-study is included which requires a small number of patients (maximum of 20 patients) to undergo a second CT scan soon after their procedure. Further, a total of 10 healthcare professionals (vascular surgeons and radiologists) will be asked to fill in an online survey, to document why they chose to use intravascular lithotripsy for these patients.

Duration of participant participation: Six months (i.e. until end of follow-up).

6.2 Primary and Secondary Endpoints/Outcome Measures

Primary outcome measure: patency of the treated arterial atherosclerotic lesion based on duplex ultrasound measurement at six months after the procedure has taken place (recorded as a binary outcome i.e. yes or no).

Secondary outcome measures:

During the inpatient stay:

Additional treatments during the index procedure, including other endovascular treatments (e.g. application of stent or drug coated balloon therapy or any other intervention deemed necessary by each operator)

All complications during the in-hospital stay:

Duration of in-hospital stay.

Thirty days after the procedure and at six months (final follow-up):

Re-intervention (open or endovascular - including re-intervention for other indications, which will be reported separately)

Lower limb amputation

Change in the treated atherosclerotic plaque consistency for patients requiring re-intervention or having additional imaging due to re-stenosis (secondary outcomes)

Patients' quality-of-life.

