11.3 The Level of Statistical Significance

A p value of <0.05 will be regarded as statistically significant.

11.4 Criteria for the Termination of the Study.

Given that this is an observational study which is recruiting patients who undergo a treatment that is already available in the NHS, we do not have specific stoppage criteria at this point in time. A Data Safety Monitoring Committee (DSMC) will convene at regular intervals, chaired by an independent specialist.

11.5 Procedure for Accounting for Missing, Unused, and Spurious Data.

The PI will be contacted at each site in case of missing or spurious data to ensure that the information collected is precise.

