11.7 Inclusion in Analysis

CONFIDENTIAL Page 24 of 35 SHOCC Study IRAS: 299307

All participants will be included in the final analysis as this is a pragmatic cohort study.

CONFIDENTIAL SHOCC Study IRAS: 299307

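### The primary outcome scores a lesion that failed and was re-opened as patent, and gives no score to patients who cannot be scanned at six months, so reported patency is likely to exceed what the index lithotripsy achieved

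*Protocol*

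**What the plan says.** Protocol section 6.2, repeated in the synopsis, gives the primary outcome as "patency of the treated arterial atherosclerotic lesion based on duplex ultrasound measurement at six months after the procedure has taken place". The score is binary. The section does not say whether primary, assisted or secondary patency is meant, and it sets no condition about procedures between the index treatment and the scan.

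The same section lists re-intervention as a secondary outcome, "including re-intervention for other indications, which will be reported separately". Amputation of the lower limb is another secondary outcome. Neither feeds into the patency score.

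On who is analysed, section 11.7 says "All participants will be included in the final analysis as this is a pragmatic cohort study". On missing data, section 11.5 says only that "The PI will be contacted at each site in case of missing or spurious data". Section 8.8 allows withdrawal for disease progression. Section 11.2 expects all 60 patients to complete follow-up with full clinical and imaging data.

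**The concern.** The primary objective (section 5) is the effect of lithotripsy on patency of the treated lesion. The study has a single arm, so the absolute patency proportion is its headline result, and section 4 presents the study as groundwork for a randomised trial.

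A status reading at one time point cannot tell a lesion that stayed open from one that closed and was opened again. Under the written rule both score yes. The second is a failure of the index procedure that a further procedure put right, and counting it as a success moves the estimate in the favourable direction only.

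The second weakness is at the other end of the outcome range. A patient who has died, or whose treated segment has been removed, cannot have the duplex. The definition gives no value for that patient, and a query to the site cannot recover a scan that could not be done. If such patients are left out of the denominator, some of the worst outcomes disappear from the primary result.

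**Working it through.** **Inputs from the protocol.** N = 60 (section 11.2); binary patency on duplex at six months (section 6.2); one-year amputation risk of 30% in chronic limb threatening ischaemia (section 4). The 60 rests on expected recruitment. No patency rate, re-intervention rate or precision target is given for the primary outcome, so there is no plan figure to reproduce.

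**Step 1: re-intervention alone.** Let *r* be the proportion with a target-lesion re-intervention and *q* the proportion of those open at six months. Patency as written minus primary patency is *r* × *q*, whatever the primary patency is. Both ranges below are assumptions.

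| *r* | *q* | *r* × *q* |
|---|---|---|
| 10% | 80% | 8 points |
| 10% | 90% | 9 points |
| 20% | 80% | 16 points |
| 20% | 90% | 18 points |

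If primary patency were 70% (also assumed), the written rule would report 70 + 8 = 78% to 70 + 18 = 88%. A wider range of 2 to 12 re-opened lesions among 60 gives 2/60 = 3.3 to 12/60 = 20 points.

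**Step 2: comparison with sampling error.** For 42/60 (70%) the exact 95% confidence interval is 56.8% to 81.2%, a half-width of (81.2 − 56.8)/2 = 12.2 points. A shift of 8 to 18 points is of the same order as the whole sampling uncertainty, and the interval would not reflect it.

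**Step 3: adding unscanned patients.** Assume 6 lesions re-opened and patent, 6 limbs amputated with no scan, and 38 of the other 48 lesions patent without re-intervention.

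- Re-intervention and amputation counted as loss of patency: 38/60 = 63.3%.
- Re-opened lesions counted as patent, all 60 in the denominator: (38 + 6)/60 = 73.3%, which is 10.0 points higher.
- Amputated limbs also omitted: 44/54 = 81.5%, a further 8.1 points (18.1 in all before rounding).

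This step depends on the unscanned patients being omitted, which the protocol does not state.

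**Step 4: how many amputations?** Applying the 30% one-year risk at a constant hazard gives 1 − 0.70^0.5 = 16.3% by six months, or 0.163 × 60 = 9.8, about 10 patients. This is an upper-end figure: the study also enrols patients with severe claudication, every patient is revascularised, and not every amputation prevents the scan.

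**Step 5: the sections side by side.** Section 11.7 puts every participant in the analysis, section 6.2 defines the outcome only through a scan, and section 11.5 offers only a query. For a patient who cannot be scanned, these three cannot all be followed.

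**The case against.** Patency regardless of re-intervention is a legitimate quantity for a pragmatic registry. Re-interventions and amputations are reported beside it, so an attentive reader could see both, and primary patency could be derived from data already planned. Handling of missing scans is often left to the SAP, which is not at hand. Section 4 says the results will help plan a trial; it does not say that six-month patency will set that trial's sample size.

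Much of this is fair. If the quantity were labelled as patency regardless of re-intervention, it could stand as a secondary result. But separate tabulation does not correct the primary figure, because a reader cannot subtract re-opened lesions from a published proportion without patient-level linkage. The definition is also fixed in the protocol: an SAP would have to add a condition that section 6.2 does not contain.

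Stronger readings are tempting but the documents do not support them:

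- A reader might infer that amputated limbs are dropped. No section says so, and section 11.7 points the other way. What is missing is a score for them; omission is a likely result, not a stated rule.
- A reader might infer that every amputation removes the scan. A femoropopliteal lesion may still be scanned after a minor or below-knee amputation. Omitting amputees raises patency only if their lesions were less often patent than the rest.
- A reader might infer that a bypassed lesion scores as patent. The outcome concerns the treated native lesion, which may still read as not patent after bypass.

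**Conclusion.** The concern holds in a limited form. Followed as written, section 6.2 scores a failed and re-opened target lesion as patent, and the reported figure is likely to exceed the patency attributable to the index procedure. Re-intervention alone adds 8 to 18 points if 10–20% of patients have a target-lesion re-intervention and 80–90% of those lesions are open at six months. The documents supply neither rate, so the direction is firmer than the size.

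Patients who cannot be scanned because of death or loss of the treated segment have no value, and sections 6.2, 11.5 and 11.7 do not fit together for them. If they are omitted, patency is probably overstated further. That part depends on an unstated handling rule and on their lesions having done worse than average. It should not be presented as a known loss of 10 of 60 patients. The point still needs correcting before analysis, because it affects the only primary outcome of a single-arm study.

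**What to change.** Amend section 6.2 and the synopsis as follows.

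1. Define the primary outcome as primary patency: the index lesion is patent on duplex at six months, with no prior re-intervention on it and no bypass of it.
2. Count target-lesion re-intervention and major amputation of the index limb before the scan as loss of patency.
3. Report on all 60 participants. For deaths and other unscanned patients, give a best/worst-case range: all counted as patent, then all as not patent. With *u* such patients the range is *u*/60 wide, for example 3/60 = 5 points or 6/60 = 10 points.
4. Report duplex patency regardless of re-intervention as a labelled secondary outcome.

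The cost is mainly wording. Re-intervention and amputation are already study outcomes. The case report form must record, up to six months, whether each re-intervention was on the index lesion, the side and level of any amputation, and the dates. This needs checking because the six-month list in section 8.3.1 has no separate item for either event, whereas the 30-day list has both. The downside for the study team is a less favourable headline patency figure.

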8.3 Data collection

8.3.1 Main study

This study wishes to obtain the following routinely collected data from the patients' medical records and conduct further analyses* on routinely performed scans at various time points during patients' routine PAD care.

Baseline (pre intravascular lithotripsy) data collection:

- 1. Demographic information (age at time of recruitment, sex).
- 2. Weight/height, resting BP (anthropometric measurements).
- 3. Rutherford stage relating to PAD presentation.
- 4. Ankle brachial pressure index.
- 5. Baseline full blood count results and routine biochemistry, including total cholesterol levels, and lipid profile.
- 6. Baseline serum creatinine and estimated glomerular filtration rate.
- 7. Chronic kidney disease status.
- 8. Diabetes status, duration of diabetes history, and current diabetes medication(s).
- 9. History of previous major cardiovascular events.
- 10. Results of cross-sectional imaging relating to the arterial vasculature e.g. duplex or computed tomographic angiography*
- 11. Smoking status.
- 12. WiFi score.
- 13. Previous operations, including a full surgical and vascular history.
- 14. All concomitant medications as reported by patients.
- 15. Anonymised minutes from multi-disciplinary team meetings relating to the patients care.

Day of procedure (Post intravascular lithotripsy) data collection:

The data collected here will relate to information obtained during the intravascular lithotripsy

- 1. Exact location of the lesion treated,
- 2. Number and size(s) of intravascular lithotripsy catheters used
- 3. Duration of intravascular lithotripsy application per arterial site in seconds
- 4. Exact anatomy (number of occlusions or stenoses) of the arterial lesions present on intraoperative angiography
- 5. Nature of the additional surgical or endovascular treatments taking place
- 6. Duration of the whole procedure
- 7. Immediate complications during the procedure and steps taken to address them (e.g. thrombectomy)
- 8. Patency of the treated lesions
- 9. Level of operators performing the procedures
- 10. Volume of contrast used during the procedure.

Day of discharge data collection:

Where available, the data collected here will relate to the period between the completion of the intravascular lithotripsy procedure and the day of discharge

- 1. Re- interventions of any nature
- 2. Amputations of any nature
- 3. Ankle brachial pressure index.
- 4. Full blood count results and routine biochemistry.

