- 5. Major cardiovascular events during inpatient stay.
- 6. Duration of inpatient stay (ward and intensive care where applicable).
- 7. Reason(s) for admission to intensive care if relevant.
- 8. Results of cross-sectional imaging relating to the arterial vasculature e.g. duplex or computed tomographic angiography (all of these are routine care).
- 9. WiFi score.
- 10. All concomitant medications.

30 day post discharge data collection:

The data collected here will relate to the time period between the procedure 30 days post discharge.

- 1. Re-intervention(s) nature and reasons why this occurred.
- 2. Amputation(s) nature and reasons why this occurred.
- 3. Ankle brachial pressure index.
- 4. Major cardiovascular events.
- 5. Results of cross-sectional imaging relating to the arterial vasculature e.g. duplex or computed tomographic angiography
- 6. WiFi score.
- 7. All concomitant medications.
- 8. Arterial duplex scan of the affected lower limb (standard of care for patients with severe limb threatening ischaemia).

Six months post discharge data collection (final follow-up):

The data collected here will relate to the time period between the procedure 6 months post discharge.

- 1. Weight/height, resting BP (anthropometric measurements).
- 2. Rutherford stage.
- 3. Ankle brachial pressure index.
- 4. Baseline full blood count results and routine biochemistry, including total cholesterol levels, and lipid profile.
- 5. Baseline serum creatinine and estimated glomerular filtration rate.
- 6. Chronic kidney disease status.
- 7. Diabetes status, duration of diabetes history, and current diabetes medication(s).
- 8. History of previous major cardiovascular events.
- 9. Results of cross-sectional imaging relating to the arterial vasculature e.g. duplex or computed tomographic angiography (all of these are routine care).
- 10. Smoking status.
- 11. Previous operations, including a full surgical and vascular history.
- 12. Results of cross-sectional imaging relating to the arterial vasculature e.g. duplex or computed tomographic angiography*
- 13. WiFi score.
- 14. Quality of life using the EuroQol-5D (EQ-5D) questionnaire.
- 15. Recording of all concomitant medications as reported by patients.

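### Section 6.2 carries only one of objective 2's four events past discharge, and the six-month collection list reuses baseline history items, leaving TIA and late events poorly captured

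*Protocol*

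**What the plan says.** Objective 2 (section 5, repeated in the synopsis) sets out to learn whether patients suffer "stroke, transient ischaemic attack, myocardial infarction, or lower limb amputation in the six months post intravascular lithotripsy". Section 6.1, under outcomes, says that "all complications during the in-hospital stay, at thirty days and six months will be documented".

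Section 6.2 splits the secondary outcomes into two blocks. The inpatient block contains "All complications during the in-hospital stay". The block for thirty days and six months contains re-intervention, lower limb amputation, change in plaque consistency in some patients, and quality of life. It has no complications entry and does not name stroke, TIA or MI.

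Section 8.3.1 lists what is collected at each time point. The discharge list asks for "Major cardiovascular events during inpatient stay", and the 30-day list has a plain item for major cardiovascular events and another for "Amputation(s) nature and reasons why this occurred". The six-month list instead asks for "History of previous major cardiovascular events" (item 8) and "Previous operations, including a full surgical and vascular history" (item 11). These match baseline items 9 and 13 word for word. The sentence introducing the six-month list ties it to the period since the procedure. Section 10.2 has all adverse events recorded on the CRF with onset dates.

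**The concern.** The outcome list does not match an objective that it should serve. Someone who builds the tables from section 6.2 would give amputation to six months but would have no entry for stroke, TIA or MI after discharge, so part of objective 2 would go unreported.

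The six-month collection list does not make up for this. An item about past history, asked at the final visit, can bring in a stroke from years before lithotripsy alongside one that followed it. Earlier cardiovascular events and operations are likely in patients with severe PAD. The explicit re-intervention and amputation items also stop at 30 days, although section 6.2 does name both as six-month outcomes.

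TIA is the weakest point. No collection list names it. The only gloss that the protocol gives for a major cardiovascular event, in section 4, covers heart attacks and strokes. A site that reads the item that way would not enter a TIA.

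**Working it through.** The plan states no figure on this point, so the check is a comparison of the sections and a count.

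**Objective 2 against section 6.2**

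| Event in objective 2 | 6.2, inpatient block | 6.2, thirty-day and six-month block |
|---|---|---|
| Stroke | within all complications | not listed |
| TIA | within all complications | not listed |
| MI | within all complications | not listed |
| Amputation | within all complications | listed |

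Carried past discharge: 1 of 4. Missing: 4 − 1 = 3 of 4.

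**The five collection lists in section 8.3.1**

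| List | Cardiovascular events | Re-intervention | Amputation | TIA named |
|---|---|---|---|---|
| Baseline | history (item 9) | operation history (item 13) | operation history (item 13) | no |
| Day of procedure | immediate complications only (item 7) | none | none | no |
| Discharge | event item (5) | item 1 | item 2 | no |
| 30 days | event item (4) | item 1 | item 2 | no |
| Six months | history (item 8) | operation history only (item 11) | operation history only (item 11) | no |

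Of the three follow-up lists (discharge, 30 days, six months), 2 of 3 have a cardiovascular item worded as an event, and 2 of 3 have explicit re-intervention and amputation items. The six-month list has none of these. TIA is named in 0 of 5 lists.

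**What can still be recovered**

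- Stroke and MI, up to 30 days after discharge: collected directly by discharge item 5 and 30-day item 4, using the gloss in section 4.
- Stroke and MI after that: six-month item 8, if read under the list's introductory sentence; adverse event records with onset dates (10.2); review of medical records at six months (Appendix A); comparison with baseline item 9.
- Amputation and re-intervention after 30 days: six-month item 11 on the same reading, compared with baseline item 13; adverse event records; record review.
- TIA at any time: adverse event records and record review, or a site's own decision to count it as a major cardiovascular event.

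**Size of one error**

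With 60 patients, one patient's event missed or wrongly counted changes a reported proportion by 1/60 = 0.0167, or 1.7 percentage points. The protocol gives no expected event rates, so the number of such errors cannot be estimated.

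**The case against.** The best defence is that objective 2 names the events and fixes the window, so section 6.2 has merely left something out. On this view nobody should take 6.2 as an instruction to stop at discharge. The point stands in part. A reader might infer that the protocol gives equal support to an in-hospital rate and a six-month rate. It does not: the objective says six months, and section 6.1 says complications are documented to six months. Section 6.1 does not itself name stroke, TIA or MI; its mismatch with 6.2 concerns the time points for complications in general. But an outcome list that omits three of an objective's four events still needs correcting, because that list is what the tables are likely to be built from.

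The second defence is that the data exist. This also stands in part. A reader might infer that objective 2 rests on adverse event records alone. The documents do not support that, given the 30-day items, the separate baseline history, the sentence introducing the six-month list and the scheduled record review. What remains is that the introductory sentence and a past-history item point in different directions, so sites may answer differently. Adverse event capture depends on what the investigator observes or the participant reports, and Appendix A has no adverse event row.

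Third, section 8.3.1 is not the data form itself. The REDCap form is not shown and may be worded better. That is a fair limit on how much harm can be claimed.

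Finally, six-month items 4 and 5 still call blood results baseline. That is a clerical slip with no bearing on complications, and no weight is placed on it.

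**Conclusion.** The point holds as a mismatch between objective 2 and the outcome list in section 6.2, made worse by the wording of the six-month collection list. Three of the four events have no outcome entry after discharge. The six-month list has no explicit event, re-intervention or amputation item, and no list names TIA. The loss falls mainly on TIA and on events after 30 days.

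The consequence is limited to descriptive secondary outcomes. The primary outcome and the sample size are unaffected, and no stopping rule depends on these events. The 1.7-point figure is the effect of a single event in 60 patients, not an estimate of bias. The conclusion assumes that the data form follows section 8.3.1, and that sites read major cardiovascular events as section 4 glosses them. If the form already asks for dated events since the procedure and names TIA, only the omission in 6.2 remains.

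It is worth correcting because the study is meant to inform a later randomised trial, and section 4 faults the earlier randomised evidence for stopping at 30 days.

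**What to change.** 1. In the thirty-day and six-month block of section 6.2, add: *Stroke, TIA, MI and other complications from the procedure to 30 days and to six months.* Assign events to these windows by the onset date already recorded under section 10.2. Keep the in-hospital entry as a descriptive line.
2. In the six-month list of section 8.3.1, reword item 8 as: *Major cardiovascular events (stroke, TIA, MI) since the procedure.*
3. Carry the 30-day re-intervention and amputation items over to the six-month list.
4. Name TIA in the discharge and 30-day cardiovascular items.

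The cost is a few CRF items and one summary table. No new visit or test is needed, because record review at six months is already scheduled. The small downside is a higher reported complication rate, since late events and TIAs will be counted.
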